3.3.2 Marizomib Supportive Care

Subjects should receive premedication for nausea or vomiting and can receive other appropriate supportive care measures as deemed necessary by the treating investigator. Suggested supportive care measures are outlined below.

Table 4: Supportive Care Measures

Condition	Supportive Care Measures
Neutropenia or neutropenia with fever	Hematopoietic growth factors are permitted for grade 4 neutropenia or neutropenia with fever and should follow American Society of Clinical Oncology guidelines for their use. Prophylactic use of growth factors is not allowed, nor can they be used to improve blood counts to allow initiation of treatment.
Nausea, vomiting	The nausea and vomiting that may occur with marizomib administration can generally be managed through the use of appropriate supportive measures, anti-emetics (e.g., 5-HT3 antagonists, benzodiazepines, prochlorperazine). Patients should be premedicated with ondansetron or prochlorperazine 60 minutes (+/- 30 minutes) prior to marizomib administration.
Diarrhea	Specific guidelines for the use of loperamide for the subacute (days after administration) form of diarrhea are provided below: Patients should not be given drugs with laxative properties. Loperamide should be started at the earliest sign of: (1) a loose stool, or (2) the occurrence of 1-2 more bowel movements than usual in 1 day, or (3) a significant increase in stool volume or liquidity.

	
Loperamide should be taken in the following manner: 4 mg at the onset of diarrhea and then 2 mg by mouth every 2 hours, around the clock until the patient is diarrhea free for at least 12 hours. Patients may take loperamide every 4 hours during the night.
 
Patients should increase fluid intake to help maintain fluid and electrolyte balance during episodes of diarrhea.

CNS Events: Confusion, ataxia, delirium and any other neurological signs or symptoms	
All Grades: When patients develop neurological symptoms during marizomib infusion, stop the infusion. Patients should be hydrated with 1 liter bolus of normal saline and should be observed for 2 hours. Brain imaging should be obtained as indicated. Educate patient not to drive and do not use heavy machinery until the neurological symptoms resolve.
 
Grade 1 or 2 AE: Refer to Table 2
 
Grade 2-3 AE: Follow guidelines for Grade 1-2 AE above, in addition;
 
 • Treat the AE with an appropriate medication if one is available. Some investigators have used quetiapine fumarate or olanzapine for hallucinations and methylphenidate for fatigue. • Dose modification as per Table 1.
Acute Kidney Injury	Hydrate with 1 liter bolus of normal saline.
Hypocalcemia	
Calcium Supplements: Calcium supplements (e.g., calcium carbonate, 500 mg PO three times daily) may be required to maintain serum calcium levels above the lower limit of normal during chemotherapy treatment. Vitamin D supplements (e.g., ergocalciferol, 400 IU PO daily) may be appropriate for persistent hypocalcemia.

3.4 QUESTIONNAIRES

The MDASI-BT and/or MDASI-SP will be administered at baseline and at the time of imaging analysis. Every attempt should be made to administer the MDASI-BT and/or MDASI-SP prior to informing the patients about the results of the imaging study. The MDASI-BT or MDASI-SP will be completed only by the patient, unless changes in vision or weakness make this difficult. If this occurs, then the caregiver or research assistant may read the questions to the patient or assist with marking the severity number or score as described by the patient.

The average time to complete these instruments is 5 minutes. Only for English speaking patients.

3.5 FOLLOW UP

3.5.1 28-Day Safety Follow-up Visit

A Safety Follow-up visit is scheduled 4 weeks (28 ± 5 days) after the last administration of Marizomib but before any new therapy is started, if possible, whichever occurs earlier. The 28-Day Safety Follow-

up visit will comprise a full assessment for safety and tumor response as appropriate, which will include assessments indicated in Study Calendar, Section 3.6.

3.5.2 Long-term Follow-up

All SAEs ongoing at the 28-Day Safety Follow-up visit must be monitored and followed up by the Investigator until stabilization or until the outcome is known, unless the subject is documented as “lost to follow-up.”

Subjects with progressive disease (PD) after the 28-Day Safety Follow-up visit, will be followed every 6 months (± 1 month) for survival (including assessment of any further anticancer therapy) by phone call or e-mail.

Subjects without PD at the 28-Day Safety Follow-up visit should continue follow up visits and tumor imaging by MRI as follows:

- every 2 months for 1 year after treatment stop date; then,
- every 3 months for 1 year; then,
- every 4 months for 1 year; then,
- every 6 months until progressive disease, lost to follow-up, or death.

3.6 STUDY CALENDAR

Procedure	Screening	Baseline ¹	Cycles 1-24 (28 \pm 3 days) ¹			28 Days FU ¹¹	Long Term FU ^{10,11}	
			Days ¹				with PD	without PD
			1	8	15			
Marizomib ²			X	X	X			
NIH Advance Directives Form ³		X						
Medical History	X							
Confirmation of Pathology	X							
Height	X							
Physical exam, neurological exam, KPS	X		X			X	X	
Weight	X		X	X ¹²	X ¹²			
Vital signs	X		X ⁴	X ⁴	X ⁴	X	X	
EKG	X	X	X ¹³	X ¹³	X ¹³			
CBC with differential	X		X ⁵	X ⁵	X ⁵	X		
Biochemical profile ⁶	X		X ⁵	X ⁵	X ⁵	X		
Amylase / lipase/CK/ GGT, LDH			X ⁵			X		
Urinalysis	X							
Serum or urine pregnancy test ⁷	X		X ⁵					
PT, INR, aPTT, fibrinogen			X			X		

Procedure	Screening	Baseline ¹	Cycles 1-24 (28+/-3 days) ¹			28 Days FU ¹¹	Long Term FU ^{10,11}	
			Days ¹				with PD	without PD
			1	8	15			
Tumor evaluation (MRI) ⁸	X	X	X			X		X
Concomitant Medications (See 6.1)		X	X	X	X	X		X
Adverse events (See 6.1)		X	X	X	X	X		X
Research blood for SNP Studies		X						
Research blood for Pharmacogenomic Studies (Cohort 1 only)		X						
Collection of archival tumor sample for research studies		X						
MDASI-BT and/or MDASI- S ⁹		X	X			X		X
Phone call or e-mail for survival/new cancer treatments							X	X

¹ Tests done at screening or baseline do not need to be repeated on baseline or Day 1 of Cycle 1 if performed in designated time frame prior to start of study drug. Time window +/- 3 days is allowed for Days 1, 8 and 15.

² 0.8 mg/m² IV.

³ All subjects will complete and sign an NIH advanced directives form which is mandatory on this study.

⁴ See section 3.2 for vital signs schedule on days of drug infusion.

⁵ Labs will be obtained within 72 hours prior to dosing

⁶ Biochemical profile: electrolytes, BUN, creatinine, AST, ALT, total bilirubin, calcium, phosphorus, albumin, magnesium, uric acid

⁷ For women of child-bearing potential only

⁸ MRI head and/or spine with gadolinium at screening/baseline and every 8 weeks after beginning of treatment. Confirmatory scans should also be obtained in 4-8 weeks period of time following initial documentation of objective response. Patients with prior therapy that included interstitial brachytherapy or stereotactic radiosurgery must have confirmation of true progressive disease at screening rather than radiation necrosis based upon either PET or Thallium scanning, MR spectroscopy, or surgical/pathological documentation of recurrent disease. After initial confirmation of progressive disease at screening, these patients will be evaluated during treatment with regular MRI.

⁹ At baseline and then within 14 days prior to each imaging study.

¹⁰ All SAEs ongoing at the 28-Day Safety Follow-up visit must be monitored and followed up by the Investigator until stabilization or until the outcome is known, unless the subject is documented as “lost to follow-up.” Subjects with PD after the 28-Day Safety Follow-up visit, will be followed every 6 months (± 1 month) for survival (including assessment of any further anticancer therapy) by phone call or e-mail.

Subjects without PD at the 28-Day Safety Follow-up visit should continue follow up visits and tumor imaging by MRI per schedule in the Section **3.5.2**

¹¹ If subjects are unable or not willing to come to NIH to for follow up visits, they will be followed by phone call or e-mail for survival, adverse events (for 1 year only) and further tumor therapy.

¹² If significant (> 3 kg) weight loss or gain is observed during a cycle.

¹³ Within 2 hours after study drug infusion and additionally any time if clinically indicated.

3.7 COST AND COMPENSATION

3.7.1 Costs

NIH does not bill health insurance companies or participants for any research or related clinical care that participants receive at the NIH Clinical Center. If some tests and procedures performed outside the NIH Clinical Center, participants may have to pay for these costs if they are not covered by insurance company. Medicines that are not part of the study treatment will not be provided or paid for by the NIH Clinical Center.

3.7.2 Compensation

Participants will not be compensated on this study.

3.7.3 Reimbursement

The NCI will cover the costs of some expenses associated with protocol participation. Some of these costs may be paid directly by the NIH and some may be reimbursed to the participant/guardian as appropriate. The amount and form of these payments are determined by the NCI Travel and Lodging Reimbursement Policy.

3.8 CRITERIA FOR REMOVAL FROM PROTOCOL THERAPY AND OFF STUDY CRITERIA

Prior to removal from study, effort must be made to have all subjects complete a safety visit approximately 28 days following the last dose of study therapy.

3.8.1 Criteria for Removal from Protocol Therapy

- Participant requests to be withdrawn from treatment (long-term follow up permitted)
- Progressive disease
- Unacceptable toxicity as defined in section **3.3**
- PI discretion
- Positive pregnancy test
- Completion of protocol therapy (24 cycles)

3.8.2 Off Study Criteria

- Death
- Patient becomes lost to follow-up
- PI discretion
- Participant requests to be withdrawn from the study

- Screen failure

3.8.3 Lost to Follow-up

A participant will be considered lost to follow-up if he or she fails to return for 3 scheduled visits and is unable to be contacted by the study site staff.

The following actions must be taken if a participant fails to return to the clinic for a required study visit:

- The site will attempt to contact the participant and reschedule the missed visit within 4 weeks and counsel the participant on the importance of maintaining the assigned visit schedule and ascertain if the participant wishes to and/or should continue in the study.
- Before a participant is deemed lost to follow-up, the investigator or designee will make every effort to regain contact with the participant (where possible, 3 telephone calls and, if necessary, a certified letter to the participant's last known mailing address or local equivalent methods). These contact attempts should be documented in the participant's medical record or study file.
- Should the participant continue to be unreachable, he or she will be considered to have withdrawn from the study with a primary reason of lost to follow-up.

4 CONCOMITANT MEDICATIONS / MEASURES

All treatments that the investigator considers necessary for a subject's welfare may be administered at the discretion of the investigator in keeping with the community standards of medical care. See also **Table 4**. All concomitant medication will be recorded on the case report form (CRF) including all prescription, over-the-counter (OTC), herbal supplements, and IV medications and fluids. If medication changes occur during the trial period, documentation of drug dosage, frequency, route and date may also be included on the CRF.

Concomitant medications that prolong the QT/QTc interval are prohibited, excluding premedication required by protocol.

NOTE: Steroids: Steroid dosage will be carefully monitored and recorded during each course of therapy and steroid dosage changes will be considered before response determinations are made.

5 BIOSPECIMEN COLLECTION

5.1 CORRELATIVE STUDIES FOR RESEARCH

This study will test for *RELA*-fusion in all study subjects. Not only is the presence of *RELA*-fusion a criterion for enrollment in the *RELA*-fusion ependymoma cohorts, it will also help us identify if the presence of this gene fusion is a predictive biomarker in treating ependymomas with a proteasome inhibitor.

In comparison to other gliomas, our understanding of the molecular characteristics of ependymomas is limited. Therefore, we will test the collected CNS tissue specimens for biomarkers (gene mutations, copy number alterations and fusions) using the neuro-oncology brain primary CNS panel as an exploratory analyses.

RNA sequencing on paraffin embedded or frozen tissue will be performed to study the expression of NF- κ B pathway.

Blood specimens will also be collected at baseline for analysis of genetic variants including single nucleotide polymorphisms to help determine if there are genetic associations with the risk of developing CNS adverse events.

In Stage 1, Cohort 1, blood samples will be collected for pharmacogenetic studies to analyze the genomic DNA and assess genotype of the most relevant drug metabolizing enzymes and transporters (DMET).

5.1.1 Tissue

In this study, archival tumor tissue will be collected from all patients and stored in the NIH Laboratory of Pathology (See section 5.2.2).

5.1.2 Blood

Blood specimens will be collected at baseline to establish a genetic association with CNS adverse events and Pharmacogenomic Studies. Samples will be sent for barcoding and initial storage to Blood Processing Core (See section 5.2.1)

Table 5: Tissue and blood specimen collected at baseline

Test/assay	Volume blood	Type of tube/ tissue sample	Collection point	Location of specimen analysis
NOB Brain Primary CNS panel		Archival tissue samples	Baseline	NIH Laboratory of Pathology
RELA fusion by IHC			Baseline	NIH Laboratory of Pathology
NF-κB pathway by RNA Sequencing			Baseline	NIH Laboratory of Pathology
Single nucleotide polymorphisms	Blood, 5 mL	EDTA (purple top) tubes	Baseline	NIH Laboratory of Pathology (Processed in [name])
Pharmacogenomic Studies by DMET Plus (Affymetrix)	Plasma, 6 mL	EDTA (purple top) tubes	Baseline (only Cohort 1)	[name]

5.2 SAMPLE STORAGE, TRACKING AND DISPOSITION

Samples will be ordered in CRIS and tracked through the Clinical Trial Data Management system. Should a CRIS screen not be available, the CRIS downtime procedures will be followed. Samples will not be sent outside NIH appropriate approvals and/or agreements, if required.

5.2.1.2 Sample Data Collection

All samples sent to the Blood Processing Core (BPC) will be barcoded, with data entered and stored in the LABrador (aka LabSamples) utilized by the BPC. This is a secure program, with access to LABrador limited to defined [name] lab personnel, who are issued individual user accounts. Installation of LABrador is limited to computers specified by [name]. These computers all have a password restricted login screen. All [name] lab personnel with access to patient information annually complete the NIH online Protection of Human Subjects course.

LABrador creates a unique barcode ID for every sample and sample box, which cannot be traced back to patients without LABrador access. The data recorded for each sample includes the patient ID, name, trial name/protocol number, time drawn, cycle time point, dose, material type, as well as box and freezer location. Patient demographics associated with the clinical center patient number are provided in the system. For each sample, there are notes associated with the processing method (delay in sample processing, storage conditions on the ward, etc.).

Sample bar-codes are linked to patient demographics and limited clinical information. This information will only be provided to investigators listed on this protocol, via registered use of the LABrador. It is critical that the sample remains linked to patient information such as race, age, dates of diagnosis and death, and histological information about the tumor, in order to correlate genotype with these variables.

5.2.1.3 Sample Storage

Barcoded samples are stored in barcoded boxes in a locked freezer at either -20 or -80°C according to stability requirements. These freezers are located onsite in the BPC and offsite at NCI Frederick Central Repository Services in Frederick, MD. Visitors to the laboratory are required to be accompanied by laboratory staff at all times.

Access to stored clinical samples is restricted. Samples will be stored until requested by a researcher named on the protocol. All requests are monitored and tracked in LABrador. All researchers are required to sign a form stating that the samples are only to be used for research purposes associated with this trial (as per the IRB approved protocol) and that any unused samples must be returned to the BPC. It is the responsibility of the NCI Principal Investigator to ensure that the samples requested are being used in a manner consistent with IRB approval.

Following completion of this study, samples will remain in storage as detailed above. Access to these samples will only be granted following IRB approval of an additional protocol, granting the rights to use the material.

If, at any time, a patient withdraws from the study and does not wish for their existing samples to be utilized, the individual must provide a written request. Following receipt of this request, the samples will be destroyed (or returned to the patient, if so requested), and reported as such to the IRB.

5.2.2 Procedures for Storage of Tissue Specimens in the Laboratory of Pathology

Tissues designated for clinical diagnostics are transported to the Laboratory of Pathology (LP) where they are examined grossly and relevant portions are fixed, embedded in paraffin and sectioned and stained for diagnostic interpretation. Unutilized excess tissues are stored for up to three months, in accordance with College of American Pathologists/Joint Commission on Accreditation of Healthcare Organizations (CAP/JCAHO) guidelines, and then discarded. Following completion of the diagnostic workup, the slides and tissue blocks are stored indefinitely in the LP's clinical archives. All specimens are catalogued and retrieved utilizing the clinical laboratory information systems, in accordance with CAP/JCAHO regulations. The use of any stored specimens for research purposes is only allowed when the appropriate

IRB approval has been obtained. In some cases, this approval has been obtained via the original protocol on which the patient was enrolled.

Duplicate tissue samples, sample size permitting, will be banked for future analysis of RELA-fusion status in the event that preliminary results suggest that further development is warranted.

5.2.3 Protocol Completion/Sample Destruction

All specimens obtained in the protocol are used as defined in the protocol. Any tumor tissue blocks or FFPE specimens that are remaining at the completion of the protocol will be stored at the Laboratory of Pathology at room temperature. The study will remain open so long as sample or data analysis continues. Samples from consenting subjects will be stored until they are no longer of scientific value or if a subject withdraws consent for their continued use, at which time they will be destroyed.

If the patient withdraws consent the participants' data will be excluded from future distributions, but data that have already been distributed for approved research use will not be able to be retrieved.

The PI will record any loss or unanticipated destruction of samples as a deviation. Reporting will be per the requirements of section 7.2.

5.3 SAMPLES FOR GENETIC/GENOMIC ANALYSIS

5.3.1 Description of the scope of genetic/genomic analysis

Genomic DNA and total RNA will be extracted from the FFPE tumor tissue sections mounted on slides, to enrich for viable tumor content, if indicated using the AllPrep DNA/RNA FFPE kit (Qiagen). The RNA will be reverse transcribed into complementary DNA (cDNA) using degenerate hexmer primer. An amplicon based sequencing library will be generated separately from the genomic DNA and cDNA by multiplex PCR using and AmpliSeq custom panel (ThermoFisher Scientific) of 869 PCR primer pairs (genomic DNA) and 69 primer pairs (cDNA) directed to detect small nucleotide variants in 52 genes, copy number in alterations in 21 genes, and fusions between 25 gene pairs that have been associated with cancer pathogenesis. RNA sequencing on paraffin embedded or frozen tissue will be performed to study the expression of NF- κ B pathway. This genetic study will consist of somatic analysis on the tumor tissue.

Blood specimens will be collected for germline DNA analysis to establish a genetic association with CNS adverse events. DNA will be analyzed for Single nucleotide polymorphisms (SNP).

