- In the first stage, we will enroll 18 patients with *RELA*-fusion ependymoma and if 4 or more patients in Cohort 1 are progression free at 6 months, we will proceed to stage 2; otherwise we will terminate the trial and conclude that marizomib is not effective.
- In the second stage, we will enroll 32 patients with non *RELA*-fusion ependymoma.
- Patients will be treated with marizomib in cycles consistent of 28 days until disease progression or a maximum of 24 cycles.

TABLE OF CONTENTS

PRÉCIS	2
TABLE OF CONTENTS	3
1 INTRODUCTION	7
1.1 Study Objectives	7
1.1.1 Primary Objective.....	7
1.1.2 Secondary Objective(s).....	7
1.1.3 Exploratory Objective(s).....	7
1.2 Background and Rationale	7
1.2.1 Background on Ependymomas	7
1.2.2 Rationale for Marizomib.....	9
1.2.3 Pre-Clinical data.....	9
1.2.4 Clinical data	11
1.2.5 Rationale for this study	12
1.2.6 Rationale for patient reported-outcomes.....	13
2 ELIGIBILITY ASSESSMENT AND ENROLLMENT	14
2.1 Eligibility Criteria	14
2.1.1 Inclusion Criteria	14
2.1.2 Exclusion Criteria	15
2.1.3 Inclusion Criteria for Pregnancy Cohort (P).....	16
2.1.4 Recruitment Strategies.....	17
2.2 Screening Evaluation.....	17
2.2.1 Screening activities performed prior to obtaining informed consent.....	17
2.2.2 Screening activities performed after a consent for screening has been signed.....	17
2.2.3 History and physical examination.....	17
2.2.4 Laboratory Evaluation	17
2.2.5 Histologic confirmation	18
2.3 Participant Registration and Status Update Procedures	18
2.3.1 Treatment Assignment Procedures (For registration purposes only):.....	18
2.4 Baseline Evaluation.....	19
3 STUDY IMPLEMENTATION	19
3.1 Study Design	19
3.1.1 Cohorts 1-4:	19
3.1.2 Cohort P – Pregnancy Related Study Procedures, Birth and Health of Child	20
3.2 Drug Administration	20
3.3 Dose Modifications	21
3.3.1 Hallucinations management.....	23
3.3.2 Marizomib Supportive Care.....	24
3.4 Questionnaires.....	25
3.5 Follow Up.....	25
3.5.1 28-Day Safety Follow-up Visit.....	25

3.5.2	Long-term Follow-up.....	26
3.6	Study Calendar	26
3.7	Cost and Compensation.....	28
3.7.1	Costs.....	28
3.7.2	Compensation	28
3.7.3	Reimbursement	28
3.8	Criteria for Removal from Protocol Therapy and Off Study Criteria	28
3.8.1	Criteria for Removal from Protocol Therapy.....	28
3.8.2	Off Study Criteria	28
3.8.3	Lost to Follow-up.....	29
4	CONCOMITANT MEDICATIONS / MEASURES	29
5	BIOSPECIMEN COLLECTION.....	29
5.1	CORRELATIVE STUDIES FOR RESEARCH	29
5.1.1	Tissue	30
5.1.2	Blood.....	30

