1.1.3 Exploratory Objective(s)

- To determine if there is a correlation with response rate to presence of the *RELA* gene fusion in pathology from surgical CNS tissue specimen.
- To assess tumor tissue for biomarkers (gene mutations, copy number alterations and fusions) using the neuro-oncology brain primary CNS panel.
- To assess expression of NF- κ B pathway using RNA sequencing on tumor tissue.
- To assess single nucleotide polymorphisms from germline DNA to establish a genetic association with CNS adverse events.

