3.2 DRUG ADMINISTRATION

Marizomib will be administered at 0.8 mg/m² IV over at least 10 minutes (+10 minutes) (see section 14.1.5).

Patients should be premedicated with ondansetron 8 mg IV or prochlorperazine 10 mg IV 60 minutes (+/- 30 minutes) prior to marizomib infusion to prevent nausea or vomiting.

The dose will be determined using the body surface area (BSA) calculated prior to each day 1 unless significant (> 3 kg) weight loss or gain is observed during a cycle. The BSA will be calculated from the height obtained at screening and the weight obtained at day 1 visit. The dose will be rounded to the nearest 0.1 mg.

On Cycle 1, Day 1, 8 and 15 vital signs will be taken within 10 minutes before the marizomib infusion and 10 (+/- 5) minutes, 30 (+/- 10) minutes, and 1 hour (+/- 15 minutes) following the marizomib infusion. For all subsequent cycles, vital signs will be assessed prior to the marizomib infusions and approximately 30 (+/- 10) minutes following each infusion.

Investigators should start assessing patients for CNS AEs (Section 8.1.6) after the first marizomib dose, although frequently these AEs do not appear until Cycle 2 or later. Dose modifications guidelines for CNS adverse events are outlined in Table 2. A scale for rating severity of hallucinations is provided in Appendix C.

Patients should be warned against driving or operating machinery if they develop CNS adverse events while receiving marizomib.

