8.2 ASSESSMENT OF SAFETY EVENTS

AE information collected will include event description, date of onset, assessment of severity and relationship to study product and alternate etiology (if not related to study product), date of resolution of the event, seriousness and outcome. The assessment of severity and relationship to the study product will be done only by those with the training and authority to make a diagnosis and listed on the Form FDA 1572 as the site principal investigator or sub-investigator. AEs occurring during the collection and reporting period will be documented appropriately regardless of relationship. AEs will be followed through resolution.

SAEs will be:

- Assessed for severity and relationship to study product and alternate etiology (if not related to study product) by a licensed study physician listed on the Form FDA 1572 as the site principal investigator or sub-investigator.
- Recorded on the appropriate SAE report form, the medical record and captured in the clinical database.
- Followed through resolution by a licensed study physician listed on the Form FDA 1572 as the site principal investigator or sub-investigator.

For timeframe of recording adverse events, please refer to section **6.1**. All serious adverse events recorded from the time of first investigational product administration must be reported to the sponsor.

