10.4.5 Exploratory Analyses

Determination of RELA gene fusion status and expression of NF- κ B pathway to correlate with clinical course of ependymoma patients treated with Marizomib using Spearman correlation and regression analysis; the levels will be compared between responders and non-responders using an exact Wilcoxon rank sum test

Impact of baseline somatic genomic profile of ependymoma on clinical response to Marizomib. The number of somatic mutations, copy number alterations and fusions obtained for each patient will be compared between responders and non-responders. This will be done using either a Fisher's exact test, Cochran-Armitage trend test, or exact Wilcoxon rank sum test depending on the distributions of values.

Regression analysis will be further used to investigate the relationship between these covariates and clinical response.

Determination of single nucleotide polymorphisms from germline DNA to correlate with CNS adverse events will be established using an exact Wilcoxon rank sum tes.

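### The exploratory SNP analysis tests CNS adverse events with a rank-sum test that has no time-at-risk term, although time on marizomib varies widely and ends at progression

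*Combined protocol and SAP*

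**What the plan says.** The objective in section 1.1.3 is exploratory: "To assess single nucleotide polymorphisms from germline DNA to establish a genetic association with CNS adverse events". Section 5.3.1 repeats the purpose: "Blood specimens will be collected for germline DNA analysis to establish a genetic association with CNS adverse events". Section 10.4.5 gives the method in one sentence: "Determination of single nucleotide polymorphisms from germline DNA to correlate with CNS adverse events will be established using an exact Wilcoxon rank sum tes". It does not say whether the CNS variable is any/none, worst grade, a count or a rate. It names no risk window, exposure term or censoring rule. The regression sentence in the same section concerns clinical response, so it does not fill the gap.

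Time on drug is set by outcome. The Précis states: "Patients will be treated with marizomib in cycles consistent of 28 days until disease progression or a maximum of 24 cycles". Section 6.1 limits adverse events recorded more than 28 days after the last dose to serious, at least possibly related ones.

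On onset, section 3.2 says of CNS events: "although frequently these AEs do not appear until Cycle 2 or later". Section 1.2.5.1 says that ataxia, gait and balance events typically come in the first or second cycle. Onset dates are recorded; under section 8.2, "AE information collected will include event description, date of onset".

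**The concern.** On an ever/never or worst-grade scale, a patient who progresses at the first 8-week scan without a CNS event gets the same score as one who stays event-free for 24 cycles. The first was observed for about two cycles, the second for two years.

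Two consequences follow. A true toxicity variant is diluted, because short-exposure carriers had little chance to show the event. And a variant that acts only on PFS gives its carriers more time to have an event, so it can look like a toxicity variant. Section 5.3.2 plans to correlate other germline genotypes with response and/or toxicity, so the protocol itself allows that variants may act on either. At stake is the reading of one exploratory objective.

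**Working it through.** The plan states no alpha, power, carrier frequency or effect size for this analysis, so there is no figure of its own to reproduce.

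**Inputs from the documents**
- N = 50 (section 10.2), or 18 if the trial stops after stage 1 (section 10.1).
- PFS6 of 0.30 (unpromising) and 0.60 (promising), section 10.1.
- MRI every 8 weeks (section 3.6, footnote 8): 56 days / 28 = 2 cycles.
- Treatment for at most 24 cycles.
- Incidence in glioblastoma studies (section 1.2.5.1): hallucinations 19–37%, confusion 17–28%.

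**Assumptions not in the documents**
- Exponential PFS, 40% carriers, two-sided 0.05, one variant.
- CNS hazard ratio 3 for a toxicity variant; progression hazard ratio 0.5 for a PFS-only variant.
- The shape of the CNS hazard over time.

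**Step 1, closed form.** With constant CNS hazard h and progression hazard λ, ignoring the 24-cycle cap, P(event on treatment) = h/(h + λ).
- PFS6 = 0.30 gives λ = −ln(0.30)/6 = 0.2007 per month.
- Incidence of 0.28 in non-carriers gives h = 0.28 × 0.2007/0.72 = 0.0780.
- Halving λ in carriers, with h unchanged, gives 0.0780/(0.0780 + 0.1003) = 0.44.

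A variant with no CNS effect thus moves observed incidence from 28% to 44%.

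**Step 2, power for a toxicity variant with no PFS effect.** Simulated trials, CNS hazard 0.10 per cycle in non-carriers for the first three cycles, progression found at 8-weekly scans. Rank-sum on ever/never is compared with log-rank on time to first event.

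| CNS hazard after Cycle 3 | Rank-sum, PFS6 0.30 / 0.60 | Log-rank, PFS6 0.30 / 0.60 |
|---|---|---|
| unchanged | about 0.58 / 0.45 | about 0.81 / 0.87 |
| close to zero | about 0.56 / 0.64 | about 0.66 / 0.71 |

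Part of the gap in the second row is discreteness of the exact test. In one run at PFS6 0.30 the exact test gave 0.594, the uncorrected chi-square 0.633 and log-rank 0.667. So 0.039 of the 0.073 gap came from discreteness.

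**Step 3, power with incidence set to the documents' range.** Non-carrier incidence 28%, PFS6 0.30, 8-weekly MRI, rank-sum against log-rank:
- constant hazard: 0.47 v 0.66
- onset from Cycle 2 on: 0.42 v 0.66
- onset in Cycles 2–6 only: 0.54 v 0.70
- onset in Cycles 1–2 only: 0.65 v 0.73

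**Step 4, false positives for a PFS-only variant.** The rank-sum test rejects in about 0.12–0.14 of trials if events accrue throughout treatment under the Step 2 hazard, falling to about 0.04–0.06 when events are front-loaded. With incidence set as in Step 3:
- constant hazard, PFS6 0.30: 0.12–0.15; over carrier frequency 20–60% and incidence 17–37%, 0.07–0.14
- onset from Cycle 2 on: 0.16–0.21 at PFS6 0.30, about 0.10 at PFS6 0.60
- onset in Cycles 2–6 only: 0.05–0.09 at PFS6 0.30, 0.04 at PFS6 0.60
- onset in Cycles 1–2 only: 0.03–0.04
- N = 18, constant hazard: 0.06–0.07

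Log-rank stays at about 0.05–0.06 for the PFS-only variant. If the variant has no PFS effect either, the exact rank-sum test rejects in 0.03–0.04 of trials.

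**The case against.** The plan does not define the CNS variable, so it cannot be said outright to ignore time: a rank-sum test could rank events per cycle. This stands, and the loss is therefore conditional on an ever/never or worst-grade variable. It does not remove the point, since the section names no exposure term.

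A reader might infer that power is always lost and that early progressors are always miscounted. The documents do not support that. Section 1.2.5.1 places ataxia-type events in Cycles 1–2, and 8-weekly imaging carries most imaging progressors through that window. If all CNS events were that early, the false-positive problem would vanish. A variant that raises both PFS and CNS risk even gains apparent power from the same bias (0.83 v 0.73).

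The widest contrast, 0.45 v 0.87, comes from a setting with about 60% incidence in non-carriers. The single-term incidences in section 1.2.5.1 are lower (headache reaches 53%), and no composite is given. The false-positive case needs a germline variant that halves the progression hazard, and nothing in the documents points to one.

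The replacement has a weakness too. Neurological decline can be recorded as a CNS adverse event or as progression (Table 6 counts worse clinical status as progression), so censoring at progression may be informative. Doses can also be reduced after CNS events (section 3.3), so cycles are not equal exposure. Both stand and call for a sensitivity analysis, not for leaving time out.

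**Conclusion.** The concern holds in a conditional form. Section 10.4.5 names a test without a time-at-risk term for an outcome whose observation time depends on PFS. With an ever/never or worst-grade variable, the cost for a toxicity variant with no PFS effect runs from large, if events accrue throughout treatment, to small, if nearly all come in Cycles 1–3. False-positive inflation for a PFS-only variant follows the same pattern. Sections 1.2.5.1 and 3.2 do not settle which case applies, so the plan should not depend on the favourable one.

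The figures rest on the assumed carrier frequency, hazard ratios and single test at 0.05; they illustrate size and do not predict this trial's SNP screen. Severity is low: the analysis is exploratory, carries no power claim, and plays no part in the decision to open stage 2 or in the efficacy claims.

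**What to change.** In section 10.4.5:
- State which CNS terms count. The list in section 8.1.6 is open-ended and does not name ataxia or gait events. Count a symptom present at baseline only if it worsens.
- Analyse time from first dose to the first such event, censored 28 days after the last dose, by log-rank or Cox score test, with a permutation p-value when carriers are few.
- Report cycles received by genotype. This shows whether exposure differs, and a permutation p-value is less secure if it does.
- State that censoring at progression may be informative, and add a sensitivity analysis restricted to a fixed early window, for example the first two cycles, which end at about the first scheduled scan.

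The cost is a paragraph of analysis text. No new data are needed: dosing dates, onset dates and baseline adverse events are already collected.
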